7.3 Pregnancy

Pregnant participants are discontinued from the study at the time pregnancy is discovered.

8.0 ADVERSE EVENT REPORTING**8.1 Definitions**

An adverse event (AE) is any untoward medical occurrence in a patient or clinical investigation participant administered a pharmaceutical product and which does not necessarily have a causal relationship with this treatment. An adverse event can therefore be any unfavorable and unintended sign (including an abnormal laboratory finding), symptom, or disease temporally associated with the use of a medicinal (investigational) product, whether or not related to the medicinal (investigational) product.

An unexpected (unlisted) adverse event is an adverse reaction, the nature or severity of which is not consistent with the applicable product information (e.g., Investigator's Brochure for an unapproved investigational product or package insert/summary of product characteristics for an approved product).

A serious adverse event (SAE) is any untoward medical occurrence that:

- results in death;
- is life-threatening;
- requires inpatient hospitalization or prolongation of existing hospitalization;
- results in a persistent or significant disability/incapacity;
 - or
- is a congenital anomaly/birth defect

Other important medical events as assessed by medical and scientific judgment may also be considered SAEs by the investigator and should be reported in an expedited fashion.

An Unanticipated Problem (UP)/New Safety Information (NSI) is defined by the UNC IRB as any incident, experience, or outcome that:

- is unexpected (in terms of nature, severity, or frequency) given (a) the research procedures that are described in the protocol-related documents, such as the IRB-approved research protocol and informed consent document; and (b) the characteristics of the participant population being studied;
- is related or possibly related to a participant's participation in the research; and
- suggests that the research places participants or others at a greater risk of harm (including physical, psychological, economic, or social harm) related to the research than was previously known or recognized.

AE attribution will be assigned according to the following scale:

- Not related: The AE is clearly not related to the study procedures (i.e., another cause of the event is most plausible and/or a clinically plausible temporal sequence is inconsistent with the onset of the event).
- Possibly related: An event that follows a reasonable temporal sequence from the initiation of study procedures, but that could readily have been produced by a number of other factors.
- Related: The AE is clearly related to the study procedures.

8.2 Reporting

The protocol-defined expedited event reporting period for this protocol is the entire study duration for an individual participant (from study enrollment until study completion or discontinuation of the participant from study participation for any reason).

All AEs defined below must be recorded on the eCRFs if any of the following criteria have been met:

- All grade ≥ 3 AEs
- All AEs that led to a change in study treatment/intervention regardless of grade
- All AES meeting SAE definition

For all of these adverse events reported or observed, the information should be recorded in the electronic Case Report Form (eCRF) for that participant and will include a full description of the event, its seriousness, its severity or toxicity grade (intensity), the relationship to the study drug, and the treatment, outcome, and sequelae of the event.

Any serious or unexpected event, which occurs to any participant in the course of his/her treatment on this study or within 30 days following cessation of treatment, must be reported within 24 hours to the principal investigator. The immediate reports should be followed promptly by detailed, written reports. Copies of these reports should be sent to:

- UNC IRB if it meets the UNC IRB UP/NSI reporting requirements
- Events that are reportable to the UNC IRB will also be submitted to the appropriate representative of the study funding source/sponsor (NC TraCS): [name], BSN, Associate Director of Regulatory, NC TraCS ([contact])

Reporting is required of all unanticipated problems/new safety information to the UNC IRB, including those which may occur after the participant has completed or has withdrawn from the study, including after study closure.

Clinically significant AEs and other problems related to vaccines will also be reported to the Vaccine Adverse Event Reporting System (VAERS), which is maintained by the FDA and CDC (<http://vaers.hhs.gov/>).

All individual AE shall be maintained by the Principal Investigator. For those events that are not reportable to the UNC IRB, a summary (i.e., not individual reports) of all adverse events that have occurred within the last approval period will be submitted to the UNC IRB at the time of continuing review.

9.0 STATISTICAL CONSIDERATIONS**9.1 General Design Issues**

This study is a single center, single arm interventional pilot study in which participants will receive two-doses of the US FDA-approved 4CMenB vaccine according to recommended administration schedule. Blood and mucosal surface specimens will be obtained at 4 study visits. The study population will include 15 individuals aged 18-25 years desiring immunization against group B *N. meningitidis* with no contraindication to vaccination and no known immune compromising medical condition or medication. Enrolled individuals who are discontinued will be replaced.

9.2 Endpoints

9.2.1 Primary Endpoints:

- Geometric mean concentration of IgG binding to *N. gonorrhoeae* strain FA1090 surface antigens (Outer-membrane vesicles) in human serum at entry visit (prior to first vaccination), and week 7 visit (2 weeks after second vaccination) determined by ELISA
- Geometric mean concentration of IgM binding to *N. gonorrhoeae* strain FA1090 surface antigens (Outer-membrane vesicles) in human serum at entry visit (prior to first vaccination), and week 7 visit (2 weeks after second vaccination) determined by ELISA
- Geometric mean concentration of IgA binding to *N. gonorrhoeae* strain FA1090 surface antigens (Outer-membrane vesicles) in human serum at entry visit (prior to first vaccination), and week 7 visit (2 weeks after second vaccination) determined by ELISA
- Frequency of CD4+ T cells expressing at least two different activation markers (IFN-g, TNF-a, IL-2, and CD107a) after in vitro stimulation with *N. gonorrhoeae* strain FA1090 Outer-membrane vesicles in circulating PBMC obtained at entry visit (prior to first vaccination) and week 7 visit (2 weeks after second vaccination) determined by flow cytometry

9.2.2 Exploratory Endpoints:

- Geometric mean concentration of IgM, IgG, and IgA binding to *N. gonorrhoeae* strain FA1090 surface antigens (Outer-membrane vesicles) in human pharyngeal secretions at entry visit (prior to first vaccination), week 5 visit (4-6 weeks after first vaccination), week 6 visit (1 week after second vaccination), and week 7 visit (2 weeks after second vaccination) determined by ELISA
- Geometric mean concentration of IgM, IgG, and IgA binding to *N. gonorrhoeae* strain FA1090 surface antigens (Outer-membrane vesicles) in human vaginal secretions (female participants) at entry visit (prior to first vaccination), week 5 visit (4-6 weeks after first vaccination), week 6 visit (1 week after second vaccination), and week 7 visit (2 weeks after second vaccination) determined by ELISA
- Geometric mean concentration of IgM, IgG, and IgA binding to *N. gonorrhoeae* strain FA1090 surface antigens (Outer-membrane vesicles) in human urine (male participants) at entry visit (prior to first vaccination), week 5 visit (4-6 weeks after first vaccination), week 6 visit (1 week after second vaccination), and week 7 visit (2 weeks after second vaccination) determined by ELISA
- Geometric mean concentration of IgM, IgG, and IgA binding to *N. gonorrhoeae* strain FA1090 surface antigens (PorB, and MtrE) in human serum at entry visit (prior to first vaccination), week 5 visit (4-6 weeks after first vaccination), week 6 visit (1 week after second vaccination), and week 7 visit (2 weeks after second vaccination) determined by ELISA
- Geometric mean concentration of IgM, IgG, and IgA binding to *N. gonorrhoeae* strain FA1090 surface antigens (PorB, and MtrE) in human pharyngeal secretions at entry visit (prior to first vaccination), week 5 visit (4-6 weeks after first vaccination), week 6 visit (1 week after second vaccination), and week 7 visit (2 weeks after second vaccination) determined by ELISA
- Geometric mean concentration of IgM, IgG, and IgA binding to *N. gonorrhoeae* strain FA1090 surface antigens (PorB, and MtrE) in human vaginal secretions (female participants) at entry visit (prior to first vaccination), week 5 visit (4-6 weeks after first vaccination), week 6 visit (1 week after second vaccination), and week 7 visit (2 weeks after second vaccination) determined by ELISA

- Geometric mean concentration of IgM, IgG, and IgA binding to *N. gonorrhoeae* strain FA1090 surface antigens (PorB, and MtrE) in human urine (male participants) at entry visit (prior to first vaccination), week 5 visit (4-6 weeks after first vaccination), week 6 visit (1 week after second vaccination), and week 7 visit (2 weeks after second vaccination) determined by ELISA
- Qualitative assessment of the presence of human IgG directed against *N. gonorrhoeae* strain FA1090 antigens (Outer-membrane vesicles, PorB, and MtrE) in human serum at entry visit (prior to first vaccination), week 5 visit (4-6 weeks after first vaccination), week 6 visit (1 week after second vaccination), and week 7 visit (2 weeks after second vaccination) determined by immunoblot.
- Frequencies of CD8+ T cells expressing functional IFN-g, TNF-a, IL-2, and CD107a after in vitro stimulation with *N. gonorrhoeae* strain FA1090 Outer-membrane vesicles in circulating PBMC obtained at entry visit (prior to first vaccination), week 5 visit (4-6 weeks after first vaccination), week 6 visit (1 week after second vaccination), and week 7 visit (2 weeks after second vaccination) determined by flow cytometry
- Frequencies of memory, activated, and proliferating CD4+ Tfh cells specific in circulating PBMC obtained at entry visit (prior to first vaccination), week 5 visit (4-6 weeks after first vaccination), week 6 visit (1 week after second vaccination), and week 7 visit (2 weeks after second vaccination) determined by flow cytometry
- The quantity of IFN-g and IL-17 secreted after in vitro stimulation with *N. gonorrhoeae* strain FA1090 Outer-membrane vesicles from circulating PBMC obtained at entry visit (prior to first vaccination), week 5 visit (4-6 weeks after first vaccination), week 6 visit (1 week after second vaccination), and week 7 visit (2 weeks after second vaccination) determined by Bio-Plex Multiplex immunoassay
- The sequence of B-cell receptors found to associate with FA1090 Outer-membrane vesicles through flow cytometry-based cell sorting will be determined using sequencing of PCR amplicons generated using primers for non-variable regions of the B cell receptor

9.3

Sample Size and Accrual

Due to the majority of the target population likely to be undergraduate students, we anticipate that enrollment will be limited to ~1 participant each month in July and August (months when student population residing in Chapel Hill is low) and that the remaining participants will be enrolled at ~6/month in September and October. All Serum and PBMC will be stored until a complete specimen set is obtained from at least 8 subjects; the serum and PBMC specimens will then be transferred to [name] laboratory at Duke University in batch for immunologic assays. We plan to enroll up to 15 subjects so we can obtain a complete specimen set at all 4 study visits for at least 8 subjects.

9.4

Monitoring

Oversight of the trial is provided by the Principal Investigator (PI). The PI will be responsible for safety monitoring throughout the study. The PI will assure that informed consent is obtained prior to performing any research procedures, that all subjects meet eligibility criteria, and that the study is conducted according to the IRB-approved research plan. Study data are accessible at all times for the PI to review. The PI will review study conduct including: accrual, drop-outs, protocol deviations after 5 participants are enrolled and complete the study protocol and then on an annual basis until study is complete. The PI reviews AEs individually in real-time and in aggregate after 5 individuals have completed the protocol and then annually until study is complete. The PI reviews and reports all serious adverse events (SAEs) and unanticipated events as defined in

section 8.0 in real-time. The PI ensures all protocol deviations, AEs, and SAEs are reported to the NC TraCS and the IRB according to the applicable reporting requirements.

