1.3 Exploratory Objectives

1. Determine whether immunization with 4CMenB induces mucosal surface antibodies against *N. gonorrhoeae* surface antigens
2. Determine whether immunization with 4CMenB induces serum and/or mucosal surface antibodies against *N. gonorrhoeae* porB or mtrE
3. Determine whether immunization with 4CMenB induces serum and/or mucosal surface antibodies against *N. gonorrhoeae* antigens other than porB and mtrE
4. Determine whether polyfunctional CD8+ lymphocytes directed against *N. gonorrhoeae* surface antigens are induced by immunization with 4CMenB
5. Determine quantity and phenotype of CD4+ Tfh cells lymphocytes induced by immunization with 4CMenB
6. Determine inflammatory cytokine production by *N. gonorrhoeae* surface antigen-stimulated PBMC from 4CMenB-immunized humans.
7. Identify and clone B-cell receptors that recognize *N. gonorrhoeae* antigens after immunization with 4CMenB

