3.0 STUDY DESIGN

This study is a single center, single arm, interventional pilot study in which participants will receive two-doses of the 4CMenB vaccine according to the recommended administration schedule and will provide blood, pharyngeal swabs, and urine or self-collected vaginal swabs at each of four study visits.

The study population will **include 15 individuals** aged 18-25 years with no contraindication to vaccination and no known immune compromising medical condition or medication.

Participants will be seen for informed consent and eligibility screening. Enrolled participants will be given 1 dose of 4CMenB at enrollment and a second dose at week 5. Participants will be seen at entry, weeks 5, 6, and 7 for blood collection, pharyngeal swabs, and provide urine (male participants) or self-collected vaginal swabs collected for secondary screening and baseline immunologic testing.

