4.0 SELECTION AND ENROLLMENT OF PARTICIPANTS

4.1 Inclusion Criteria

1. Able to understand and give informed consent
2. Willingness to undergo all study procedures.
3. Males or females between the ages of 18 to 25 at screening (inclusive).
4. Good health, as determined by medical history and targeted physical exam.
5. Participants agree to abstain from vaccines from study entry to 30 days after receipt of the second 4CMenB vaccine.
6. Female participants of child bearing potential must have a negative urine pregnancy test at the screening visit, and prior to receipt of vaccines at study entry and week 5 visits. Self-reported history is acceptable documentation of hysterectomy, bilateral oophorectomy, tubal ligation, or tubal micro-inserts which eliminate child bearing potential of participant. If participating in sexual activity that could lead to pregnancy, women must agree to use a form of contraceptive until 28 days after completion of the vaccine series. At least one of the following methods must be used appropriately: Condoms (male) with or without spermicidal agent, Diaphragm or cervical cap with spermicide, Intrauterine device (IUD), or Hormone-based contraceptive. Self-report of a monogamous male partner who has a vasectomy is also acceptable.

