6.0 CLINICAL AND LABORATORY EVALUATIONS**6.1 Schedule of Events**

Evaluation	Screening	Entry	48-72 hr post injection	Post-Entry Evaluations			
				Week 5	48-72 hr post injection	Week 6	Week 7
Medical & medication history	X	X		X		X	X
Acute Illness Assessment		X		X			
Vital signs/targeted physical exam	X	X		X		X	X
Pregnancy test ^{1a}	X	X		X			
Phlebotomy collected blood (up to 60 mL per visit)		X		X		X	X
Stored PBMCs ²		X		X		X	X
Stored serum ²		X		X		X	X
Pharyngeal swab collection ²		X		X		X	X
Self-collected vaginal swab ^{1,2}		X		X		X	X
Urine collection ^{2,3}		X		X		X	X
Vaccine injection		X		X			
Telephone contact			X		X		

¹ female participants only^{1a} female participants of child bearing potential² mucosal surface swabs, urine, serum, and PBMC preparations will be used for immunologic analysis that will be conducted on batched samples.³ male participants only**6.2 Timing of Evaluations****6.2.1 Screening Evaluations**

Screening evaluations include: medical history, medication history within the past 60 days, vital signs, targeted physical exam, and pregnancy test for female participants of child bearing potential). Screening visit must be conducted no greater than 30 days prior to enrollment visit. The screening evaluation and enrollment visit can all occur on the same day. Participants may be re-screened one time.

6.2.2 *Entry Evaluations*

Entry evaluations will be collected PRIOR to phlebotomy, specimen collection, and vaccine administration:

Acute Illness Assessment will be completed before phlebotomy, specimen collection, and vaccine administration. Participants who have an acute illness may be rescheduled for their phlebotomy, specimen collection, and vaccine within their screening visit window.

Update medical history and concomitant medications. Conduct a targeted physical exam and collect vital signs [heart rate (HR), blood pressure (BP), oral temperature (Temp), respiration rate (RR), and weight] prior to phlebotomy to collect up to 60 mL of blood, specimen collection, and vaccine administration.

For females of reproductive potential, negative urine pregnancy testing results must be available before phlebotomy, specimen collection, and vaccine administration.

Samples to be stored for immunologic testing will be batch run at the end of the study: pharyngeal swabs, urine sample (from male participants), self-collected vaginal swabs (from female participants), serum, and PBMC.

6.2.3 *Post-Entry Evaluations*

Week 5 Evaluations:

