Acute Illness Assessment will be completed before phlebotomy, specimen collection, and vaccine administration. Participants who have an acute illness or who have taken exclusionary anticoagulant medications may be rescheduled for their vaccine within their screening visit window.

Update medical history and concomitant medications before phlebotomy and vaccine administration. Conduct a targeted physical exam and collect vital signs (HR, BP, Temp, RR) before phlebotomy to collect up to 60 mL of blood, specimen collection, and vaccine administration.

For females of reproductive potential, negative urine pregnancy testing results must be available before phlebotomy, specimen collection, and vaccine administration.

Week 5 laboratory evaluations will be collected PRIOR to vaccine administration:

Samples to be stored for immunologic testing will be batch run at the end of the study: pharyngeal swabs, urine sample (from male participants), self-collected vaginal swabs (from female participants), serum, and PBMC.

Week 6 and Week 7 Evaluations:

Update medical history and concomitant medications prior to phlebotomy to collect up to 60 mL of blood and specimen collection.

Samples to be stored for immunologic testing will be batch run at the end of the study: pharyngeal swabs, urine sample (from male participants), self-collected vaginal swabs (from female participants), serum, and PBMC.

6.2.4 *Discontinuation Evaluations*

Participants who elect not to receive or cannot receive the initial immunization or second immunization within the appropriate study time window are permanently discontinued from the study and will have no further evaluations conducted upon discontinuation. Participants who remain eligible but elect to prematurely discontinue from the study will have no additional evaluations performed from the point at which they discontinue. Participants who experience a grade 3 or 4 Adverse Event related to the vaccine or study procedures prior to the second immunization will be discontinued from the study and will return for evaluation at week 6 and/or 7 to ensure resolution but will not provide specimens for immunologic evaluation.

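### Menstrual blood on the self-collected vaginal swabs is neither recorded nor handled in the analysis, so with at most 8 women the exploratory vaginal antibody results can be distorted by chance and cannot be untangled later.

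*Combined protocol and SAP*

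**What the plan says.** The first exploratory objective in 1.3 is: "Determine whether immunization with 4CMenB induces mucosal surface antibodies against" gonococcal surface antigens. In women, 9.2.2 serves it partly through vaginal swabs. One endpoint is the geometric mean concentration of IgM, IgG and IgA binding to FA1090 "surface antigens (Outer-membrane vesicles) in human vaginal secretions (female participants) at entry visit (prior to first vaccination". A parallel endpoint covers "surface antigens (PorB, and MtrE) in human vaginal secretions (female participants) at entry visit (prior to first vaccination". Both are repeated at weeks 5, 6 and 7.

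On timing, section 3.0 states: "Participants will be seen at entry, weeks 5, 6, and 7 for blood collection", with the swabs taken at the same visits. Section 6.3.5 gives windows: day 35 ± 7 for week 5 (vaccine as late as 8 weeks), then 5-9 and 12-16 days after the second dose. All of them run from vaccination dates.

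The swab footnotes in 6.1 deal with sex and batching: "mucosal surface swabs, urine, serum, and PBMC preparations will be used for immunologic analysis that will be conducted on batched samples". The grounds for rescheduling are, at entry, "Participants who have an acute illness may be rescheduled for their phlebotomy, specimen collection, and vaccine within their screening visit window", and at week 5, "Participants who have an acute illness or who have taken exclusionary anticoagulant medications may be rescheduled for their vaccine". The history list in 6.3.1 asks about past sexually transmitted infection but not about menses. Section 6.3.4 goes from elution to ELISA and describes no check for blood. Section 9.5.1 analyses the four-visit outcomes by GEE over time, with no term or exclusion for blood.

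**The concern.** Blood on a swab brings serum antibody with it. The primary hypothesis is that serum antibody rises, so a given amount of blood adds more gonococcus-binding antibody after vaccination than before. In a woman who bleeds at week 7 but not at entry, the serum response can pass for a vaginal one. In a woman who bleeds at entry but not at week 7, a real local rise can be hidden.

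Section 9.5.2 says that no published data exist on these antibodies in mucosal secretions after 4CMenB, and that the study is to supply baseline values and variability for later trials. Unexplained variation from blood damages that product. The assays are run in batch at the end of the study, so bleeding status that was not written down at collection cannot be reliably recovered when the results come in.

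**Working it through.** The plan states no power, variance or effect size for the vaginal endpoints, so there is no figure of its own to reproduce. The check sizes the gap.

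**Inputs from the documents**
- Nominal visit days 0, 35, 42 and 49 (3.0, 6.3.5).
- At most 8 women (4.3), so 7 or 8 if all 15 participants enrol.
- 80% intervals (9.5.1).
- Serum fold rise R, taken from the geometric midpoints of the two intervals in 9.5.2: √(25,906 × 90,811) = 48,503 and √(49,228 × 126,115) = 78,793, so R = 1.62. This is whole-cell strain 1291 after three doses, so it is only a stand-in for FA1090 vesicles after two.

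**Assumptions not in the documents**
- Natural 28-day cycle, random phase at entry, M = 5 days of bleeding (range 3-7).
- x = blood-borne antibody relative to local antibody on a bloody swab before vaccination, range 0.5-10.
- No true local response.
- SD of log change without blood 0.5.

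**1. How often.** Per swab, M/28 = 3/28, 5/28, 7/28 = 11%, 18%, 25%. Modulo 28, the visits fall at offsets 0, 7, 14 and 21. With up to 7 days of bleeding the four exposures do not overlap, so 4 × 5/28 = 71% of women have one affected swab (43% at 3 days, 100% at 7). Simulating cycles of 21-35 days, bleeding of 3-7 days and the protocol windows gives 63%.

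**2. Imbalance between entry and week 7.** On these days a woman never bleeds at both visits, so P(week 7 only) = M/28. For k women, P(at least one) = 1 − (1 − M/28)^k:

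| Days of bleeding | 7 women | 8 women |
|---|---|---|
| 3 | 55% | 60% |
| 5 | 75% | 79% |
| 7 | 87% | 90% |

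Bleeding at entry only has the same probabilities and acts in the opposite direction.

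**3. Average bias.** The expected week 7/entry ratio is [(1 + Rx)/(1 + x)]^(M/28). At M = 5:
- x = 0.5: (1.81/1.50)^(5/28) = 1.03
- x = 1: (2.62/2)^(5/28) = 1.05
- x = 10: (17.25/11)^(5/28) = 1.08
- limit for large x: 1.62^(5/28) = 1.09

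The limit is 1.05 at 3 days and 1.13 at 7 days. If serum does not rise, the ratio is 1.00.

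**4. One affected woman.** If she bleeds at week 7 only, her apparent rise is 1 + Rx = 2.6-fold (x = 1) to 17-fold (x = 10). She alone moves the geometric mean ratio of 7 women to 2.62^(1/7) = 1.15 up to 17.25^(1/7) = 1.50 (8 women: 1.13-1.43).

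**5. Precision, M = 5, 7 women.** The variance that blood adds to the log change is (5/28)[ln²(1 + Rx) + ln²(1 + x)] minus the squared mean, which gives SD 0.50 at x = 1 and 1.57 at x = 10. The half-width multiplier of the 80% interval is exp(t × SD/√7) with t = 1.44 on 6 df:
- no blood: exp(1.44 × 0.50/√7) = 1.31
- x = 1: total SD √(0.25 + 0.25) = 0.71, multiplier 1.47
- x = 10: total SD √(0.25 + 2.47) = 1.65, multiplier 2.45

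The blood-driven change is not normal, so these are guides to size.

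**The case against.** The strongest reply is that blood is as likely on the entry swab as on the week 7 swab, so most of the effect cancels on average. That stands: step 3 gives an expected ratio of only 1.03-1.09 at 5 days. A reader might infer that serum antibody will routinely be counted as a mucosal response; the figures do not support that. What cancellation on average does not do is protect a single sample of at most 8 women, and steps 2, 4 and 5 concern that sample.

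Several other limits also stand. The bleeding length and x come from outside the documents. Hormonal contraception, which 4.1 accepts, would lower the rates. Visits have windows, so the swabs are not at rigidly fixed weeks, though no window is tied to bleeding. The endpoints are exploratory, in a pilot that declares its power unknown. A laboratory manual might hold collection rules, but none is among the documents.

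A reader might also infer that objective 1 cannot be answered in women. The documents do not support this: women also give pharyngeal swabs at all four visits, and same-day serum is assayed, which gives context although it does not identify the source.

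Finally, because 4.1 accepts methods such as "Diaphragm or cervical cap with spermicide", a reader might extend the point to intercourse or vaginal products. Section 4.1 only lists these among several options, and nothing in the documents gives a mechanism or a size for such an effect.

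**Conclusion.** The omission is real, and it weakens the vaginal part of the exploratory objectives. Under a natural 28-day cycle with 3-7 days of bleeding, 11-25% of vaginal swabs fall in menses, and imbalance between entry and week 7 in at least one of 7-8 women is more likely than not (55-90%; 75-79% at 5 days). The systematic bias is small. The damage is chance imbalance and wider intervals: the 80% multiplier goes from 1.31 to 1.47-2.45 for 7 women under the stated values of x and SD. The primary serum and CD4+ endpoints are untouched.

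It might seem to follow that swabs should be moved to non-bleeding days, or that flagged swabs should be dropped by default. Neither is supported. Entry and week 5 specimens precede vaccination, so moving them would shift a dose or need an extra visit. The week 6 and week 7 windows span only five days. Default exclusion at 5 days of bleeding would leave 7 × 8/28 = 2 of 7 women with all four swabs, and 7 × 18/28 = 4.5 of 7 with an entry/week 7 pair.

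**What to change.** In 6.2.2, 6.2.3 and 6.3.4, record two items at each vaginal collection: current bleeding (yes/no) and visible blood on the swab (yes/no). Take the swab as scheduled and leave visit and vaccination timing unchanged.

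In 9.5.1, prespecify that both sets of vaginal endpoints (vesicles; PorB and MtrE) are reported for all swabs and again without blood-flagged swabs, each with its 80% interval and the number of women contributing. State that a vaginal rise will be described as mucosal only if it persists without the flagged swabs, and define in advance what counts as persisting. Because the second set is smaller, compare the point estimates as well as the intervals, so that lost precision is not read as a lost response.

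The cost is two eCRF items, one extra analysis, and a smaller set of swabs behind the blood-excluded result. The items have to be in place before collection, because they cannot be reliably reconstructed when the batch is assayed.
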